11.9. Pulmonary Function Tests

The following pulmonary function tests (PFT) are performed at screening and Week 10: forced expiratory volume in 1 second (FEV₁), forced vital capacity (FVC), percent of predicted FEV₁, percent of predicted FVC, and if locally available, diffusion capacity of the lung for carbon monoxide (DLCO). Summary tables including actual values, change, and percent change from Baseline will be presented for PFT results by visit (Baseline, Week 10, last available

measurement while on treatment during IP). DLCO results in domestic unit (mL/min/mmHg) will be converted to SI unit (mmol/min/kPa) prior to analysis using the following conversion factor:

- $\text{DLCO in SI unit} = (\text{DLCO in domestic unit}) / 2.986$

Patients with at least one FEV_1 or $\text{FVC} < 70\%$ predicted will be listed showing all PFTs observed across all visits. Data collected on the DLCO eCRF will be listed separately.

[REDACTED]

[REDACTED]

[REDACTED]

[REDACTED]

[REDACTED]

[REDACTED]

[REDACTED]

[REDACTED]

[REDACTED]

[REDACTED]

[REDACTED]

[REDACTED]

[REDACTED]

[REDACTED]

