13.4.3. Safety Analyses

All safety analyses will be carried out on the Safety population.

Adverse events will be monitored during the trial and the data analyzed with respect to incidence within each treatment group as well as severity and potential relationship of the AEs to investigational drug. Adverse events with onset on, or after the first dose of investigational drug or with onset prior to the first dose of investigational drug that increase in severity on, or after the first dose of investigational drug will be considered treatment-emergent. Treatment-emergent AEs will be summarized for the Safety population by System Organ Class and Preferred Term, and presented in descending order of frequency within each System Organ Class. Serious AEs and AEs leading to discontinuation will be summarized similarly.

Associated laboratory parameters such as hepatic profile, renal function, and hematology values will be grouped and presented together. For each laboratory test, individual patient values outside the standard reference range will be flagged and listed. Shift tables will be produced showing the frequency of shifts from Baseline to the lowest and to the highest on-trial value in and out of the normal range as well as by visit. Changes from Baseline to each visit for each laboratory parameter will also be summarized.

The change from Baseline to each visit for each of the vital sign variables will be summarized. Abnormal vital sign values will be flagged and listed.

The change from Baseline to each visit for each of the ECG parameters will be summarized. An outlier analysis of ECG results will be conducted.

The change from Baseline for each of the PFT parameters will be summarized. An outlier analysis of PFT results will be conducted.

OCT parameters will be summarized.

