11.4. Clinical Laboratory Evaluations

Laboratory assessments will be performed by a central laboratory. All summaries will be based on the standard international (SI) units provided by the central lab. Each patient's hematology, blood chemistry, and urinalysis values will be flagged as "low", "normal", or "high" relative to the normal ranges of the central laboratory. Results from certain laboratory assessments are blinded as per Section 6.7.

Summary statistics of observed values, change and percent changes from Baseline in numeric laboratory parameters will be provided by visit (Baseline, Week 5 [hematology/chemistry/pregnancy only], Week 10, highest value post-baseline during IP, lowest value post-baseline during IP, last available measurement while on treatment during IP). For each laboratory parameter, frequency summaries of categorical shifts from Baseline to each post-Baseline time point (Week 5 [hematology/chemistry/pregnancy only], Week 10, and last available measurement while on treatment during IP) will be provided. For select laboratory parameters (ALC, ANC, WBC, AST, ALT), frequency summaries of patients with abnormalities will be summarized by visit (Baseline, Week 5 [hematology/chemistry/pregnancy only], Week 10, last available measurement while on treatment during IP) and overall.

All laboratory data will be listed, including unscheduled/repeat visits. Unscheduled visits will be included in the calculation of Baseline, highest/lowest/last available on treatment/anytime post-Baseline value.

For each laboratory test, individual patients with any values outside the standard reference range will have all their test results listed.

Hematology

The following laboratory parameters will be included in hematology summary tables: red blood cell (RBC) count, total and differential white blood cell (WBC) count (basophils, eosinophils, lymphocytes, monocytes, and neutrophils), platelet count, hemoglobin (HGB), hematocrit, mean corpuscular volume (MCV), mean corpuscular hemoglobin (MCH), and mean corpuscular hemoglobin concentration (MCHC).

The number and percentage of patients with abnormalities in hematology assessments, defined as $ALC < 200$ cells/ μ L, $ALC < 500$ cells/ μ L, $ANC < 1,000$ cells/ μ L, and total WBC $> 20,000$ cells/ μ L will be summarized overall and by visit post-Baseline. Patients with at least one abnormality in ALC, ANC or total WBC defined above will be listed.

Blood Chemistry

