The following laboratory parameters will be included in the blood chemistry summary tables at the screening visit: sodium, potassium, chloride, calcium, magnesium, phosphate, blood urea nitrogen (BUN), glucose, hemoglobin A1c, albumin, alkaline phosphatase, creatinine, alanine aminotransferase (ALT), aspartate aminotransferase (AST), gamma glutamyltransferase (GGT), total bilirubin, conjugated bilirubin, total cholesterol, triglycerides, high-density lipoprotein (HDL), low-density lipoprotein (LDL), and C-reactive protein (CRP). For all other visits the tests will include BUN, hemoglobin A1c, albumin, alkaline phosphatase, creatinine, ALT, AST, GGT, total bilirubin, conjugated bilirubin, and CRP.

The number and percentage of patients with abnormalities in ALT and AST, defined as $> 1 \times$ ULN, $\geq 2 \times$ ULN, $\geq 3 \times$ ULN, $\geq 4 \times$ ULN, $\geq 5 \times$ ULN, $\geq 8 \times$ ULN, and $\geq 10 \times$ ULN will be summarized by overall and by visit post-Baseline.

Patients with at least one ALT or AST that is $\geq 3 \times$ ULN will be listed showing all LFTs (ALT, AST, total bilirubin, direct bilirubin, alkaline phosphatase, and GGT) observed across all visits.

Evaluation of drug-induced serious hepatotoxicity (eDISH) plots of maximum ALT/AST values versus Total Bilirubin will be presented for assessment of potential Drug Induced Liver Injury (DILI). Total bilirubin value will be taken from the same visit at which maximum ALT/AST is observed. If maximum ALT/AST is reached at multiple visits, then the highest total bilirubin value from those visits will be plotted.

Urinalysis

The following laboratory parameters will be included for urinalysis: leukocytes, specific gravity, bilirubin, blood, glucose, ketones, pH, protein, and urobilinogen.

Serum pregnancy and serology testing

Serum β -human chorionic gonadotropin (hCG) will be collected at Screening for females of childbearing potential. Serology testing will also be collected at Screening and will include immunoglobulin G (IgG) antibodies to varicella-zoster virus (VZV), human immunodeficiency virus (HIV), immunoglobulin M (IgM) antibodies to hepatitis A virus (HAV), surface antigen of the hepatitis B virus (HBsAG), anti-hepatitis B core total antibodies (anti-HBc total), hepatitis B virus deoxyribonucleic acid (HBV DNA), and anti-hepatitis C virus (HCV) IgG/IgM.

Serum pregnancy results and serology testing results at Screening will be listed only.

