11.5. Vital Sign Measurements

Systolic and diastolic blood pressure (SBP and DBP) and pulse (HR) will be assessed in a sitting position and collected at each visit. On Day 1 of treatment for the IP, careful cardiac monitoring of the patients is required. Resting pulse and blood pressure in the sitting position will be measured before the first dose of investigational drug and every hour for at least 6 hours thereafter. For the hourly measurements after investigational drug administration, HR and sitting blood pressure will be measured once and recorded in the eCRF. The first dose monitoring strategy should also be repeated at Day 5 or at Day 8 if any cardiac safety issues were observed on the previous Day of dose escalation.

Summary statistics of actual values and changes from Baseline in vital signs will be provided by visit (Baseline, Week 5, Week 10, highest value post-baseline during IP, lowest value post-baseline during IP, last available measurement while on treatment during IP). On Day 1, hourly

changes from predose up to hour 6 in blood pressures and HRs will be summarized for all patients.

Patient's lowest heart rate during 6-hour cardiac monitoring on Day 1 will be summarized by number and percentage by category: ≥ 65 , 60-64, 55-59, 50-54, 45-49, 40-44, 35-39, < 35 bpm, as well as < 40 bpm and < 45 bpm.

The number and percentage of patients requiring extended cardiac monitoring beyond hour 6 on Day 1 or requiring monitoring on Study Days 5 and/or 8 will be summarized by Day: Day 1, Day 5, and Day 8. A listing of these patients will be presented that shows the hourly change from the pre-dose assessment at each of the available Baseline, Study Day 5, and Study Day 8 visits by patient for HR and blood pressures.

The number and percentage of patients with clinically relevant abnormalities defined below will be summarized overall and by visit (Week 5, Week 10, last available while on treatment during IP) and overall. The denominator will be the number of patients with observed data at both Baseline and respective post-Baseline visit, unless specified otherwise.

- SBP:
 - > 140 mmHg post-Baseline
 - > 160 mmHg post-Baseline
 - > 180 mmHg post-Baseline or an increase from baseline of > 40 mmHg
 - > 180 mmHg post-Baseline (denominator will be the number of patients with Baseline SBP ≤ 180)
 - an increase from Baseline of > 40 mmHg
 - < 90 mmHg post-Baseline or a decrease from Baseline of > 30 mmHg
 - < 90 mmHg post-Baseline

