11.8. Electrocardiograms

Electrocardiograms will be performed before and 6 hours after the first dose of investigational drug administration for all patients on Induction Day 1 while the patient is in the clinic. The 6 hour postdose ECG will be evaluated by the treating physician, with input if needed from a local cardiologist or a central reader to confirm if extended monitoring is required. Additional ECG monitoring will be performed on Days 5 and 8 if cardiac issues are identified on the prior day of dose escalation.

Summary tables including actual values and change from Baseline will be presented for ECG results by visit (Baseline, Day 1 Hour 6, Week 10, last available measurement while on treatment during IP). An ECG outlier analysis will be performed by visit (Baseline, Day 1 Hour 6, Week 10, last available measurement while on treatment during IP) and overall showing the proportion of patients with QT > 450 milliseconds (ms), QT > 480 ms, QT > 500 ms, QTcF > 450 ms, QTcF > 480 ms, QTcF > 500 ms, change from Baseline in QT of >30 ms, change from Baseline in QT of >60 ms, change from Baseline in QTcF of >30 ms, and change from Baseline in QTcF of >60 ms. The overall interpretation of the ECG results (normal; abnormal, probably non-significant; and abnormal, possibly significant) will be summarized in the same table. The denominator will be the number of patients with result (actual value or change) at the respective visit.

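### The induction SAP gives the promised outlier analysis of pulmonary function only as a patient listing, with no count by arm and no cut-off on change from Baseline

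*SAP*

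**What the plan says.** Protocol 13.4.3 (Safety Analyses) asks for a summary of change from Baseline in PFT parameters and then, as a separate commitment, states "An outlier analysis of PFT results will be conducted". The ECG paragraph just above is worded the same way: "An outlier analysis of ECG results will be conducted".

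SAP 11.9 (Pulmonary Function Tests) covers the first commitment: "Summary tables including actual values, change, and percent change from Baseline will be presented for PFT results by visit". For individual patients, its visible text provides a listing of anyone with at least one FEV1 or FVC below 70% "predicted will be listed showing all PFTs observed across all visits", and a separate listing of DLCO data. No other PFT cut-off appears there.

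Other safety data are treated differently:

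- **ECG (SAP 11.8):** "An ECG outlier analysis will be performed by visit", giving the proportion of patients over named limits for QT and QTcF, both absolute and as change from Baseline.
- **Vital signs (SAP 11.5):** "The number and percentage of patients with clinically relevant abnormalities defined below will be summarized overall and by visit", again with absolute and change limits.
- **Hematology (SAP 11.4):** "The number and percentage of patients with abnormalities in hematology assessments, defined as" stated ALC, ANC and WBC limits.
- **Liver enzymes (SAP 11.4):** "The number and percentage of patients with abnormalities in ALT and AST, defined as" multiples of the upper limit of normal.

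SAP 11 makes presentation by treatment/cohort the default for safety analyses, with individual listings in addition.

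**The concern.** The protocol makes one promise for two kinds of measurement, and the SAP carries it out in two ways. For ECG it becomes a rate per arm. For PFT it becomes, as far as can be seen, a list of patients.

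Pulmonary effects are adverse events of special interest (Protocol 12.2.6). Appendix 3 of the protocol reports mild early reductions in FEV1 and DLCO in multiple sclerosis patients and concludes that they do not amount to a risk. Cohort 1 offers a randomized placebo comparison that could check this in ulcerative colitis. The question is how many patients per arm had a large fall, and none of the visible outputs answers it:

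- Tables of change show the average shift and, through the minimum and maximum, the extremes.
- SAP 11.2 counts adjudicated pulmonary events as reported on the adverse event form, so a fall in FEV1 or FVC that nobody reported as an adverse event is not counted.
- A listing has no denominator.

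**Working it through.** The plan states no figure to reproduce here. The check compares the texts, works out what the 70% rule captures, and illustrates what a listing or a table of means can hide.

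**1. Text comparison.** The protocol lists the outlier analysis in addition to the change summary, so the change tables in SAP 11.9 do not fulfil it. The only other candidate in the visible section is the listing below 70% of predicted. The SAP does not itself call that listing an outlier analysis; the link is inferred.

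**2. What the 70% rule captures.** Exclusion criterion 39 (Protocol 8.2) bars entry with FEV1 or FVC below 70% of predicted at Screening, so patients start at 70% or more. Holding the predicted value fixed, the fall needed to be listed, as a fraction of Baseline, is more than 1 − 70/Baseline.

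| Baseline, % of predicted | Fall needed to be listed |
|---|---|
| 100 | 1 − 70/100 = 30.0% |
| 90 | 1 − 70/90 = 22.2% |
| 87.5 | 1 − 70/87.5 = 20.0% |
| 80 | 1 − 70/80 = 12.5% |
| 72 | 1 − 70/72 = 2.8% |

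- A patient going from 100 to 75 loses 25/100 = 25% and is not listed, because 75 is above 70.
- A patient going from 72 to 68 loses 4/72 = 5.6% and is listed.

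Protocol Appendix 3 triggers evaluation when a parameter is below 70% of predicted and also below 80% of baseline. The two conditions cross at 70/0.8 = 87.5% of predicted. Anyone starting below 87.5% can be listed without being below 80% of Baseline. SAP 11.9 keeps the first half of the trigger and drops the second.

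**3. Raw counts under 2:1 allocation.** The arm sizes are the planned 400 and 200 (Protocol 13.1). The event counts are assumed; the documents give none. Intervals are Newcombe 95% limits for a difference in proportions, built from the Wilson limits (l, u) of each arm: lower = d − √[(p1 − l1)² + (u2 − p2)²], upper = d + √[(u1 − p1)² + (p2 − l2)²].

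| RPC1063 vs placebo | Rates | Difference (points) | 95% CI |
|---|---|---|---|
| 12 vs 6 | 3.0% vs 3.0% | 0.0 | −3.6 to 2.7 |
| 12 vs 1 | 3.0% vs 0.5% | 2.5 | −0.1 to 4.7 |
| 12 vs 0 | 3.0% vs 0.0% | 3.0 | 0.7 to 5.2 |

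For 12 vs 6, the Wilson limits are 1.72% to 5.17% and 1.38% to 6.39%. The lower limit is 0 − √(1.28² + 3.39²) = −3.62 and the upper is √(2.17² + 1.62²) = 2.71. A list with twice as many active patients as placebo patients therefore shows no difference in rate.

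**4. What a table of means can miss.** Suppose the 12 patients each lose 25 points of percent-predicted FEV1 and nobody else changes on average. The active mean moves by 12 × 25/400 = 0.75 points. The standard error of the difference in means is SD × √(1/400 + 1/200).

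| Assumed SD of change (points) | Standard error | 0.75 / standard error |
|---|---|---|
| 8 | 0.69 | 1.08 |
| 10 | 0.87 | 0.87 |
| 12 | 1.04 | 0.72 |

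The shift is 0.7 to 1.1 standard errors, which would not stand out. The same 12 patients against 0 on placebo give a difference in proportions whose interval excludes zero.

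**The case against.** The strongest objection is redaction. Blacked-out text follows the last visible sentence of SAP 11.9, the contents entries after that section are also hidden, and the appendices on visit windows cannot be read. A PFT outlier table could be there. This limits what can be claimed, and the fix is conditional for that reason. Still, the visible text of 11.9 runs without a break from its first sentence to the listings.

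Second, the protocol does not say what an outlier analysis must contain, and listing everyone past a fixed limit is a form of outlier review. That is fair, so this is a weak design choice and not a proven breach. But the SAP shows by its treatment of ECG how it reads the same words.

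Third, maintenance has its own SAP, which may contain such counts, and induction has only one scheduled PFT after Baseline. This stands as a limit on scope. A maintenance table would not supply the randomized induction comparison.

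Fourth, physical examination results are also listed only (SAP 11.6). The protocol makes no outlier commitment for those.

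Fifth, much is already reported by arm: change tables, pulmonary events of special interest, and discontinuations, which should pick up many patients below 50% of predicted because that value requires stopping treatment. These overlap with the proposed table but give no rate of large falls.

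Finally, the event counts, fall size and SDs above are assumed, and Protocol Appendix 3 reports 645 patients admitted to Cohort 1, not 600. At about 430 versus 215, 12 versus 0 becomes 12/430 = 2.8 points. The conclusion is unchanged.

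**Conclusion.** The concern holds for the visible text of the induction SAP. The protocol's PFT outlier analysis is reduced to a listing with no by-arm count or percentage and no change-based limit. Its single cut-off catches losses just over 2.8% in some patients and misses losses of up to 30% in others. The listing and change tables together do not give the rate of large falls on RPC1063 against placebo.

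The consequence is confined to induction safety reporting; alpha, power, endpoints and data collection are unaffected. The threshold arithmetic rests only on limits stated in the protocol and SAP. The illustrations of rates and means rest on assumed inputs. The change should be made, with moderate confidence because of the redaction.

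**What to change.** Add one table to SAP 11.9, by treatment/cohort and for Total RPC1063 1 mg, with n (%) of patients whose worst on-treatment FEV1 or FVC during induction is:

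- (a) below 70% of predicted;
- (b) below 80% of Baseline;
- (c) both (a) and (b) for the same parameter, which is the evaluation trigger in Protocol Appendix 3;
- (d) below 50% of predicted, the stopping rule in Protocol 12.2.6.

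The denominator is patients with a Baseline and at least one post-Baseline value. Row (b) catches the fall from 100% to 75% that the listing misses, and row (c) leaves out the fall from 72% to 68%. One set of worst-value rows is enough, because scheduled induction PFTs are at Screening and Week 10 only. Keep the listing as support.

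The cost is one more table from data already collected. No visit, test, patient or protocol amendment is needed. If the redacted text already contains such a table, nothing has to change.
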